We propose a RCT of TF-CBT that builds on our feasibility study, with the goal of testing the effectiveness of an intervention that is locally feasible, acceptable, and holds promise for improving mental health outcomes and functioning of orphaned children. Although 8 RCTs of TF-CBT have been conducted in the US, there has never been a RCT of its effectiveness in LAMICs with high prevalence of HIV. The proposed trial, to be conducted in both Moshi, TZ and Bungoma, KE ($N = 640$, with 20 TF-CBT groups provided in each region), includes: (1) a usual care control group in each region, (2) independent research interviewers; and (3) enhanced ecological validity and local responsibility by including the lay counselors from the feasibility study to assist [name] and [name] in training and supervising the lay counselors.

3C2a. Outcomes Examined. We plan to examine clinical outcomes, which include CTG, PTS, PTSD, depressive symptoms, behavioral problems, as well as any effect on the child-guardian relationship and the child's overall daily functioning (the last of these is a tool to be developed locally in the first quarter of the study; see Tables 3 & 4). We also plan to describe and examine the impact of implementation factors (e.g., TF-CBT fidelity, lay counselor knowledge gain, guardian and child attendance) on clinical outcomes. With the increasing attention given to task-shifting approaches³² and their promise for reducing the mental health treatment gap, implementation efforts that incorporate feasible methods for building greater local responsibility and sustainability are needed.

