The proposed study is a rigorous test of clinical outcomes building on a training and supervision approach employed by [name] (consultant on this study)^{33,34}, [name]^{35,76}, and others³⁵ in RCTs in other LAMICs. This approach involves local, trained lay individuals (i.e., our feasibility study lay counselors) who act as the direct treatment model supervisors, under supervision themselves, by TF-CBT and mental health experts (i.e., [name] & [name]). Our team views this RCT as the first step in a broader research plan to test the effectiveness of TF-CBT in successive implementation stages that systematically increase local expertise and responsibility and decrease expert involvement, with the goal of enhancing our knowledge around effective, feasible, and sustainable implementation strategies in LAMICs. As stated in the recently released NIH/PEPFAR RFA, focused on HIV/AIDS specifically (i.e., RFA-AI-11-003): "scientific advances regarding the implementation of effective interventions have not kept pace."

3C2b. The comparison group for the RCT is a "usual care" (UC) condition (i.e., existing orphan support services; (see Section 3C3c for our preliminary studies on UC in TZ & KE; also see Human Subjects). We enroll 320 child-guardian dyads in each of the two conditions (TF-CBT & UC; 640 total), with half of the participants enrolled in TZ and half in KE (see Table 2). Both sites are mixed urban and rural areas, allowing testing of TF-CBT in both settings to examine any impact of setting variables (i.e. differences in UC; urban vs. rural) on clinical outcomes or implementation (e.g., fidelity, attendance). Equal numbers of males and females, and children in age groups 7-10 and 11-13 will be recruited for both TF-CBT and UC. In the POFO study we easily recruited nearly twice this number (e.g., 560) in each region, indicating that the population of OAC in the areas in which we plan to recruit are high enough to support the proposed sample.

Sample size estimates for the RCT were determined using effect sizes from TF-CBT RCTs conducted in the US^{81,104}, from outcomes obtained in our TZ feasibility trial, and data from the Zambia TF-CBT feasibility trial (see Section 3C5b; for Power Analyses). Each site has a local UC group to enhance internal validity, given unique cultural, historical, political, religious, and ethnic differences, including relatively recent election riots experienced in KE.

	Moshi, TZ		Bungoma, KE	
	Urban	Rural	Urban	Rural

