We will test hypotheses through a standard approach to model-building, focusing on creating parsimonious explanatory models through progressive taxonomies as follows^{122,123}. An unconditional model (i.e. one without predictors) of the outcome will be fitted first, which allows specification of the random effects, which in turn provides an estimation of the amount of interdependence at each level of clustering. For longitudinal models including multiple time points (i.e. client outcomes from baseline to follow up assessments), an unconditional growth model will be fit to identify time trends and inter-individual variance in trends. We will next test the effects of the primary variable of interest (e.g., condition assignment, or therapist fidelity to treatment model) on the outcome in a conditional model (i.e., one with predictors). Finally, theoretically relevant covariates will be

added to determine the robustness of the main effects. Relative goodness-of-fit for each successive model will be evaluated using likelihood ratio tests and deviance statistics.

3C5b. Primary Analyses

Aim 1. Test the effectiveness of a group model of TF-CBT for orphaned youth in two East African countries, including any variation by child age and gender.

Hypothesis 1: Children in the TF-CBT condition will demonstrate greater reductions in symptoms and greater improvement in overall functioning and the child-guardian relationship.

These analyses focus on whether TF-CBT produces significant reductions in symptoms (i.e. CTG, PTS, depression, behavioral problems) or improvement in functioning, or the child-guardian relationship compared to UC. Hypotheses will be tested in two ways using MLM. First, we test whether the TF-CBT condition differs from the UC condition at 12-weeks (i.e., end of TF-CBT). This hypothesis will be tested with a simple 2-level MLM, predicting the observed outcome (by child or guardian report) at 12-weeks, while accounting for clustering of individuals within TF-CBT groups, for the TF-CBT condition. The general Level 1 equation, which models individual differences in symptoms at 12-weeks, would be as follows:

Level 1:	$Symptoms_{ig} = B_{0g} + B_{1g}PreSx + B_{2g}Cov + e_{ig}$
Level 2:	$B_{0g} = \pi_{00} + \pi_{01}Treatment + r_{00}$ $B_{1g} = \pi_{10} + r_{00}$ $B_{2g} = \pi_{20}$

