For example, where the outcome is the level of symptoms for a given client i in group g ; B_{0g} (the intercept) represents the average 12-weeks level of symptoms for all children in a given group g , B_{1g} is the effect of pre-treatment symptoms, B_{2g} is the effect of

child/guardian-level covariates (such as demographics: child age, gender), and e_{it} represents residual variance in the outcome for individual i in group g . If randomization was effective, the effects of pre-treatment symptoms may be ignored. The Level 2 equations represent how the coefficients at Level 1 are distributed across treatment groups. Both the intercept and the effects of pre-treatment symptoms (if needed) would be specified as random variables, which would allow their effects to differ across treatment groups. The level 2 equation would follow the general form of $B_{0g} = \pi_{00} + \pi_{01}Treatment + r_{00}$, which uses condition-level variables (such as assignment to TF-CBT or UC) to predict how effects differ. Thus the hypothesis that group-based TF-CBT produces significant improvements in symptoms over the UC condition would be tested by evaluating the significance of π_{01} above, which tests the effects of condition assignment on 12-week symptoms.

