3C5c Power. Power analyses were conducted using Optimal Design 2.0¹²⁴. A primary concern when estimating power in HLM focuses on the Interclass Correlation Coefficient (ICC) for providers, as providers are nested within conditions. Higher positive ICCs result in less statistical power, and few estimates of provider ICCs for fidelity to treatment are available. A review of 20 studies predicting client functioning found provider ICCs clustering from -0.1 to .06¹²⁵. Because precise estimates for ICCs are unknown, we examined ICC thresholds within a range of effect sizes (with .05 Type I error rate, power of .80, 8 children per TF-CBT group; 320 children total). Estimates did not include the effect of covariates which, if moderately correlated with the outcome variable, will increase statistical power. Therefore, these estimates present a conservative estimate. Our primary hypothesis test (i.e. differences at 12-weeks between TF-CBT & UC) is sufficiently powered ($1-\beta = .80$) to detect small effects (.35) with ICCs up to .15, moderate effects (.50) with ICCs up to .30, and all conceivable large effects. For detecting condition differences in terms of the linear or quadratic slope, analyses suggested that the proposed *N* has power ($1-\beta = .80$) to detect effects as small as .29 on slopes. Finally, for Aim 3, the current sample of 320 individuals in the TF-CBT condition, the current study is sufficiently powered to detect small (.21) effects of individual implementation variables on outcomes, but with only 20 clusters (i.e., groups) the study will have less power to detect all but large effects of group-level variables (e.g., fidelity).

3C6. Rationale of Choices Made in the Research Design. Our team carefully considered various design and methodological challenges, our rationale for various decisions is discussed here.

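### The printed Aim 1 model gives usual-care children a group random effect that the prose reserves for TF-CBT, so the standard error of the primary test is right only if the two arms have equal total variance

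*Combined protocol and SAP*

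**What the plan says.** 3C5a describes children as nested in groups in the TF-CBT condition. 3C5b (Aim 1) says the 12-week model predicts the outcome "while accounting for clustering of individuals within TF-CBT groups, for the TF-CBT condition".

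The printed model is:

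- Level 1: Symptoms_ig = B_0g + B_1g PreSx + B_2g Cov + e_ig
- Level 2: B_0g = π_00 + π_01 Treatment + r_00; B_1g = π_10 + r_00; B_2g = π_20

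The explanation below it repeats the intercept equation ("The level 2 equation would follow the general form of" the same expression) and states that "Both the intercept and the effects of pre-treatment symptoms (if needed) would be specified as random variables". The treatment effect is judged by the significance of π_01, and 3C5c calls the 12-week difference the primary hypothesis test.

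The plan does not say what g is for a UC child. It gives no arm-specific variance, no robust standard error and no degrees-of-freedom method. The three-level growth model is built by adding a level to this one.

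**The concern.** The prose and the equation describe different models. In the prose, only TF-CBT children share a group effect. In the equation, r_00 is not multiplied by Treatment, so every child has one, and the single e_ig at Level 1 implies one residual variance for both arms.

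One natural way to run the printed model is to make each UC child a cluster of one. The total UC variance must then equal τ² + σ², the same sum as in TF-CBT. The estimates of τ² and σ² are pulled by the scatter of 320 UC children who carry no information about group effects. The error passes straight into the standard error of π_01, and so into the primary p-value.

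Two smaller defects sit in the same lines. The symbol r_00 serves for both the intercept and the baseline slope, and a baseline slope that varies by group has no meaning for children without a group.

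**Working it through.** **Inputs.** Arm sizes are from 3C2b: "We enroll 320 child-guardian dyads in each of the two conditions". The number of groups is from 3C2: "with 20 TF-CBT groups provided in each region", so 2 × 20 = 40 groups, and 40 × 8 = 320 children. The ICCs are from 3C5c, which cites a literature range up to .06 and claims power "to detect small effects (.35) with ICCs up to .15, moderate effects (.50) with ICCs up to .30".

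**The plan's own power figure.** 3C5c states its basis as "with .05 Type I error rate, power of .80, 8 children per TF-CBT group; 320 children total". Scale the total variance to 1 in each arm and let x = ICC + (1 − ICC)/8. For a partially nested comparison, SE² = x/G + 1/n_UC.

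- 40 groups against 320 UC, effect .35, ICC .15: x = .15 + .85/8 = .25625. SE² = .25625/40 + 1/320 = .00953, SE = .0976, power .938.
- Same layout, effect .50, ICC .30: x = .3875, SE² = .3875/40 + 1/320 = .01281, SE = .1132, power .991.
- 20 groups of 8 against 320 UC: power .749 and .885 (normal approximation .792 and .915).

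None of the layouts tried gives .80 for both pairs. 3C5c also counts clusters differently ("but with only 20 clusters (i.e., groups") from the 40 that 3C2 implies. The point below does not depend on this figure.

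**Printed model, UC children as singletons.** Set TF-CBT total variance to 1. The true quantities are then W = 1 − ICC within groups, B = ICC + (1 − ICC)/8 for group means, and U = the UC/TF-CBT variance ratio. The expected REML criterion to minimise over σ² and τ² is

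280[ln σ² + W/σ²] + 39[ln(τ² + σ²/8) + B/(τ² + σ²/8)] + 319[ln(τ² + σ²) + U/(τ² + σ²)].

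Model SE² = (τ² + σ²/8)/40 + (τ² + σ²)/320. True SE² = B/40 + U/320. Type I error ≈ 2Φ(−1.96 × model SE/true SE).

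*Example, ICC .15, U = 0.5.* The fit gives σ² = .660 and τ² = .080. Model SE = .0798. True SE = √(.25625/40 + .5/320) = .0893. The SE ratio is .894 and type I error is about .080.

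Model SE / true SE, with approximate type I error in brackets:

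| UC/TF-CBT variance | ICC .05 | ICC .06 | ICC .15 | ICC .30 |
|---|---|---|---|---|
| 0.26 | 0.93 (.067) | 0.92 (.070) | 0.85 (.097) | 0.76 (.136) |
| 0.5 | 0.96 (.061) | 0.95 (.063) | 0.89 (.080) | 0.83 (.104) |
| 1 | 1.00 (.050) | 1.00 (.050) | 1.00 (.050) | 1.00 (.050) |
| 1.5 | 1.06 (.038) | 1.08 (.035) | 1.19 (.020) | 1.23 (.016) |
| 2 | 1.42 (.005) | 1.44 (.005) | 1.48 (.004) | 1.46 (.004) |

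Simulation (3,000 runs per cell) gave type I error of .064, .100 and .136 at ratio 0.27 for ICC .05, .15 and .30, and .015, .005 and .005 at ratio 2. A partially nested analysis with arm-specific variances and Satterthwaite degrees of freedom stayed between .041 and .055 throughout.

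**Other codings the plan leaves open.** With all UC children as one group and equal variances, the SE is 2.7 times too large at ICC .05 and 4.8 times at ICC .30. With invented UC groups of 8, the SE ratio is 1.00 at ICCs of .05 to .30, but that coding contradicts the prose.

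**What the pilot shows.** End/baseline variance ratios from the feasibility table (3C1d) are:

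- traumatic grief: 9.66²/4.97² = 3.78
- depression: 5.30²/5.79² = 0.84
- SDQ: 6.28²/6.64² = 0.89

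**The case against.** The prose states the right nesting twice, and the equations are offered as a general form. 3C5a specifies random effects from an unconditional model and compares later models by likelihood ratio, and the random baseline slope applies only if needed. A careful analyst could therefore fit the correct model. The reused r_00 may be a typing or extraction slip, since other subscripts in the section are also irregular. The common residual variance is implied by a missing arm index in Level 1; the plan nowhere states it. Singleton coding is an assumption.

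Most of this stands as a limit on size. It does not remove the conflict: the equation is the only written model for the primary test, and an unconditional model over both arms also needs a g for UC children.

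Three stronger readings are tempting, and the documents do not support them.

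- *The pilot shows that TF-CBT will be 3.78 times as variable as UC.* That is a before/after ratio in one treated, uncontrolled sample of 32, and the other two outcomes give 0.84 and 0.89. Entry cut-offs may also narrow the baseline spread, so UC variance could rise too.
- *The false-positive rate will be inflated.* This needs UC to be less variable, which is unknown. If TF-CBT only adds group variance to a shared residual, the SE ratio is .996, .965 and .892 at ICC .05, .15 and .30.
- *The primary test will be underpowered.* With UC variance twice that of TF-CBT and the plan's .35 effect in pooled SDs, power under the printed model is about 92% at ICC .05 and 82% at ICC .15, against 99% and 97% for the correct SE. Precision is lost, but power stays above .80.

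**Conclusion.** The contradiction is real and affects the primary test. Under singleton coding, the standard error of π_01 is correct only when the arms have equal total variance. The direction of any error cannot be predicted from the documents.

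Its size is conditional. In the ICC range the plan cites (up to .06) and for ratios of 0.26 to 1.5, it is small: about 8% or less in the SE, with type I error at most about .07. It becomes material at the ICCs of .15 and .30 that the plan uses for power, or when UC is twice as variable (42% to 48% too large at ICCs from .05 to .30).

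These results assume 40 complete groups of 8, 320 UC children, no dropout, two-sided testing at .05, and variances taken after any baseline adjustment. The variance ratios are assumptions, because no UC standard deviation is given. This should be corrected before the data are analysed. It does not show that the planned result would be wrong.

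**What to change.** Replace the Level 2 equations with a partially nested model:

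- B_0g = π_00 + (π_01 + r_0g) × Treatment, so that the group effect exists only in TF-CBT;
- B_1g = π_10, a fixed baseline coefficient, as the Aim 3 model already has;
- a separate variance for e_ig in each arm.

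State how UC children are coded; with the Treatment multiplier the coding no longer drives the fit. Name Satterthwaite or Kenward-Roger degrees of freedom. Carry the same structure into the three-level growth model, so that group-level variation in intercept and slope is limited to TF-CBT.

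The cost is a rewritten equation and one extra variance parameter. With equal variances the two approaches agree, so nothing material is lost. Settling it before outcome data are seen also removes an analyst's choice over the primary p-value.

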If children are eligible and assent and consent are provided, remaining baseline assessment measures are administered (see Table 4) and participants are randomized. Randomization procedures occur prior to the screenings by the local PC and Drs. [name] and [name], reducing any randomization bias. Interviewers have a numbered stack of consent forms that are used in numerical order. Each consent form includes an attached envelope with randomization status (see Human Subjects for more information). Guardian-child dyads randomized to TF-CBT begin the 12-week group protocol within 2 weeks. All dyads are assessed again at 12-14 weeks post-baseline, 6-months, and 12-months post baseline. For all assessment meetings, children and guardians receive a small incentive for participation costing <\$2.50, (e.g., bag of sugar, laundry soap, pen).

Table 4. Study Measures (All Measures are included in Appendix A)

Domain; Respondent ^A	Measures & Indicators	Interval [*]	
Demo-graphics; G	Demographic Survey. We assess pertinent demographic information (e.g., guardian characteristics, years caring for child, home situation) using an established demographics measure from POFO, also used in the feasibility study. † +	BL, 12w, 6M, 12M	
Clinical Outcomes	Posttraumatic Stress; C, G	UCLA PTSD Index for DSM-IV¹⁰⁸ (UCLA PTSD-RI). The 38-item UCLA PTSD RI assesses trauma exposure and PTS symptoms. Response choices for PTS items are 0 - 4. The UCLA PTSD RI demonstrates good convergent validity and good to excellent test-retest reliability. Cronbach’s α in the range of .90. †	BL, 12w, 6M, 12M
	Behavioral Difficulties; G	Strengths & Difficulties Questionnaire¹⁰⁷ (SDQ). The SDQ is a brief behavioral screening survey (ages 3-16) with 25 items on 5 scales (Emotional Symptoms, Conduct Problems, Hyperactivity/Inattention, Peer Relationship Problems, & Prosocial Behavior). Response choices are from 0-2. The SDQ has been shown to have good discriminant validity and acceptable levels of test-retest reliability ¹⁰⁸ and a Cronbach’s α of .73 ¹⁰⁹ . †	BL, 12w, 6M, 12M
	Childhood Traumatic Grief, C	The UCLA Trauma Psychiatry Service Grief Inventory , (TPSG) is a 10-item measure that includes a subset of the items on the Expanded Grief Inventory ¹¹⁰ and is used to assess CTG symptoms. The scale has demonstrated moderate - high levels of internal validity, and has been used successfully with children aged 6 and older. †	BL, 12w, 6M, 12M

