To test how TF-CBT influences trajectories of symptoms over time (e.g., 6-months, 12-months), analyses may be expanded to incorporate multiple times of assessments by adding a third level to the above model to test a growth curve model in the MLM framework. Because there are expected to be no differences across conditions at pre-treatment, the intercept could be fixed to the final time point (12-months), allowing two related but distinct questions to be tested: (1) does TF-CBT predict lower levels of symptoms at 12-months; and (2) does TF-CBT produce greater changes (reductions) in symptoms over time than receipt of usual care? The general Level 1 equation would then represent an individual's level of symptoms at a given time point, Level 2 equation would represent individual differences in the Level 1 equation, and Level 3 would represent group differences in the Level 2 equations. Thus the new Level 1 equation would be: $Symptoms_{itg} = B_{0ig} + B_{1ig}Time + e_{itg}$, representing Symptoms at time t for individual i in group g , B_{0ig} being the level of symptoms at Time 0, and B_{1ig} being the effects of Time on symptoms (i.e. the rate of change in symptoms over time). Both the intercept and slope would be allowed to randomly vary across individuals, allowing their prediction from individual level variables (such as pre-treatment symptoms or covariates). For example, the Level 2 equation for the effects of Time would be $B_{1ig} = \pi_{00} + \pi_{01}Cov + r_{00}$. Finally, effects at Level 2 would also be allowed to randomly vary across groups, allowing us to model the effects of condition on the level of symptoms at the final time point, and on the rate of change over time.

It may be that there are significant individual differences in symptoms at 12-weeks, but that these differences do not continue to increase or are not maintained. The hypothesis of decreasing gains for the TF-CBT condition would be tested by adding a quadratic component to the linear growth model. Specifically, the quadratic effect (of time, represented as $time^2$) would test whether there are decelerations in the rate of change in symptoms from baseline to the 12 month outcome, and whether there are individual differences in those decelerations.

Aim 2. Examine any differences in clinical or implementation outcomes for country (TZ; KE) or setting (urban, rural), including differences in receipt of usual care.

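### The growth model permits the pre-treatment score to be both its first outcome and a predictor of intercept and slope; if that option is used, the slope standard error comes out about 3% to 17% too large

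*Combined protocol and SAP*

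**What the plan says.** Section 3C5a describes the longitudinal models as covering "client outcomes from baseline to follow up assessments". Section 3C5b, Aim 1, adds a quadratic term to look for "decelerations in the rate of change in symptoms from baseline to the 12 month outcome". Both make the baseline score one of the modelled outcomes.

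The Level 1 growth equation is linear in time, "representing Symptoms at time t for individual i in group g", with one residual term and no separate treatment of the baseline visit. The random intercept and slope are then opened to child-level predictors, "allowing their prediction from individual level variables (such as pre-treatment symptoms or covariates"; the pre-treatment score is the first example named.

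The growth analysis is introduced permissively: "analyses may be expanded to incorporate multiple times of assessments by adding a third level to the above model". The one Level 2 slope equation written out contains only a generic covariate. The remark in 3C5b that pre-treatment symptoms may be disregarded if randomisation worked belongs to the 12-week model, so it does not settle the question here.

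**The concern.** Conditional on itself, a child's baseline score has no variance left. A growth model with that score as first outcome row and as Level 2 predictor still assigns the row the same residual variance as every other visit. The random effects must compensate, and they can do so only up to the limit at which a variance or correlation ceases to be admissible.

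Two things are at stake. The standard error for the arm difference in slope no longer describes the sampling variation of the estimate. And measurement error in the baseline score enters the fitted slope and the predictor with opposite effect, so the baseline-by-time coefficient is non-zero even when expected change is unrelated to severity.

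**Working it through.** **Inputs from the plan.** Visits: "All dyads are assessed again at 12-14 weeks post-baseline, 6-months, and 12-months post baseline" (3C4d), taken as 0, 3, 6 and 12 months. 640 children, 1:1 (3C2b). Alpha .05, power .80 and a detectable slope effect of .29 (3C5c); two-sided testing is assumed.

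**Assumed, because the plan gives no variance components.** Baseline variance 1; reliability (stable share of baseline variance) .3 to .8, so residual variance s2 = 1 − reliability; slope SD 0 to .08 per month; intercept-slope correlation −.5 to +.3. Plateau and autoregressive patterns were also tried. Clustering by TF-CBT group and dropout were left out.

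**1. The plan's own figure.** The .29 cannot be reproduced, since its slope variance, reliability and ICC are not stated. With (1.96 + .84) × sqrt(4/N), 640 independent children give .22 and 320 give .31. Eighty clusters of 8 with an assumed ICC of .10 give 2.80 × sqrt(4 × (.10 + .90/8)/80) = .289. Nothing below depends on it.

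**2. Weight of the baseline visit in a child's fitted line.** Mean time = 5.25; sum of squares = 27.5625 + 5.0625 + .5625 + 45.5625 = 78.75. Weight in the slope: −5.25/78.75 = −1/15. Weight in the intercept at time 0: 1/4 + 5.25²/78.75 = .60. Moving the time origin to 12 months does not change the slope results.

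**3. Artefact in the baseline-by-time coefficient.** With no true link between severity and slope, the expected coefficient is −s2/15 per month:

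| Reliability | Per month | Over 12 months (SD per SD of baseline) |
|---|---|---|
| .3 | −.047 | −.56 |
| .5 | −.033 | −.40 |
| .7 | −.020 | −.24 |
| .8 | −.013 | −.16 |

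**4. Why the fit reaches the boundary.** Take reliability .5 and no slope variance. The covariances of fitted intercept and slope with baseline are .5 + .5 × .60 = .80 and −.5/15 = −.033. After baseline is removed, the implied intercept variance is .5 − .80² = −.14 and the implied slope variance is 0 − .033² = −.001. Neither is admissible. Over reliability .3 to .8 the smallest eigenvalue runs from −.22 to −.05. The constrained fit gives an intercept-slope correlation of 1.00.

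**5. Effect on the slope standard error.** With exchangeable correlation the unadjusted slope variance is s2/78.75, and true adjustment removes (s2/15)². So adjusted SE / unadjusted SE = sqrt(1 − .35 × s2). The second column comes from fitting the constrained random intercept-and-slope likelihood; the third is the product of the first two; the fourth is 2 × (1 − Φ(1.96 × ratio)).

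| Assumed correlation | True adjusted / unadjusted | Model / true adjusted | Model / unadjusted | Type I error |
|---|---|---|---|---|
| Exchangeable .3 | .869 | 1.17 | 1.02 | .02 |
| Exchangeable .5 | .908 | 1.16 | 1.05 | .02 |
| Exchangeable .7 | .946 | 1.15 | 1.09 | .02 |
| Autoregressive .6 per visit | .81 | 1.07 | .87 | .04 |

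Over the wider set (random slopes, plateau trajectories, slower autoregressive decay) model / true adjusted runs from 1.03 to 1.17 and type I error from about .02 to .045. Simulated trials of 640 children gave ratios of 1.04 to 1.16. The 12-month level SE is inflated by .2% to 2.6%.

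**6. Without the pre-treatment predictor.** The ratio is 1.00 in every random-slope scenario. One exception is unrelated to the dual use: with the pilot traumatic grief SDs (4.97, then 9.66) it is 1.08 to 1.10 without the predictor and about 1.14 with it. There the baseline-by-time coefficient runs from −.028 to +.024 per month, so even its sign is not fixed.

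**7. Power, one example** (reliability .5, slope SD .02, effect set to give .80 without the predictor): .79 under the dual use, against .87 with a valid SE for the same adjusted estimator.

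**The case against.** The strongest reply is that the plan permits this model but does not commit to it. The growth analysis is optional, the pre-treatment score is one example in a list, and no growth equation shows it. Section 3C5a also tests condition first and adds covariates afterwards as a robustness check, so the main arm-by-time test could well come from the sound model. The primary comparison is at 12 weeks, where baseline is not an outcome. All of this stands and limits the weight of the point. It does not remove it: the option is named, nothing warns against it, and an analyst who takes it gets a wrong standard error.

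Three stronger readings are tempting, and the documents do not support them.

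- **That the detectable slope effect of .29 becomes about .34 (.29 × 1.16).** Section 3C5c computed .29 without covariates, whereas 1.16 is relative to the smaller SE of the adjusted estimator. Against the unadjusted SE the factors are 1.02, 1.05, 1.09 and .87, so .29 would move to between about .25 and .32.
- **That a quarter of the sample is in effect discarded (1 − 1/1.16² = .26).** This mixes the same two reference points. Against the unadjusted growth model, power with zero intercept-slope correlation is about .75 to .82 rather than .80.
- **That the plan would report faster improvement in more severe children.** No aim or hypothesis concerns baseline severity; Aim 1 names age and gender. The coefficient would be a nuisance term.

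**Conclusion.** Wrong as written, conditional on the named option being used. In that case the slope SE is about 3% to 17% too large for the adjusted estimator, and the test is conservative. The gain that 3C5c expects from covariates is lost under exchangeable correlation and reduced under autoregressive correlation. The baseline-by-time coefficient mixes artefact with any real relation and cannot be interpreted.

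The treatment slope estimate remains unbiased and no false efficacy claim follows. The 12-week primary model and the growth model without this predictor are not affected.

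The sizes rest on assumed variance components, independent Level 1 residuals of constant variance, and a random-effects matrix constrained to be admissible, as the plan's equations imply. The direction of the SE error held in every structure examined; the size did not.

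**What to change.** State in 3C5b that the baseline score enters each longitudinal model once only, by one of two routes.

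1. Keep baseline as the first outcome, with a common mean across arms, and delete pre-treatment symptoms from the Level 2 predictors. Removing the predictor is what restores the SE ratio to 1.00. With strictly linear time and a common baseline mean, the 12-month difference is just 12 times the monthly slope difference, so the plan's two growth questions become one test unless the quadratic term or visit-specific means are kept.
2. Use baseline as a covariate and start the outcome series at 12 weeks. In simulation with a true value of zero, the baseline-to-slope coefficient was then +.003 over 12 months (SE .055), against −.41 (SE .047) under the dual use. The slope now describes change after the end of treatment, and the plan should say so.

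The same rule should apply where Aims 2 and 3 extend these models. The cost is a sentence or two of text, with no new data or software.
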